Our successful pilot intervention Changing Oral Health Norms and Hygiene Practices among Vulnerable Older Adults supported by NIDCR #R34 DE022271 (2011-2013) was based on Fishbein's modified theory of reasoned action called Integrated Model (IM) of Behavioral Prediction (Fishbein, 2008) operationalized through Adapted Motivational Interviewing (AMI) and Bandura's notions of self-efficacy and skills reinforcement operationalized through Practice-to-Mastery or PM (Liska, 1984; Connor, 2010). The pilot study was conducted in a single building of approximately 200 apartments in the Greater Hartford Area. It included two components offered sequentially, a face to face intervention (the AMI) with practice of oral hygiene skills to mastery (PM), and two campaign fairs promoted by a small committee of building residents. Post intervention, participants (n=30) demonstrated a significant improvement in the Plague Scores from a mean score at baseline of 84% (sd=11.8%) to 58% (sd=31.2%) at follow-up (p<0.001) and the Gingival Index from a mean baseline score of 1.2 (sd=0.56) to a mean follow-up score of 0.54 (sd=0.47), p<0.001. Differences in P-M skills scores from pre to post instruction in brushing and flossing, part of the AMI-PM session showed significant improvement. Brushing scores increased from 1.9 (fair/poor) prior to the AMI-PM session to 2.9 (good/excellent; p<0.001) after and flossing skills improved from 1.7 to 2.7 (p<0.001). In the intervention group, we found significant mean decreases (improvements) from pre to post in several important cognitive domains including perceived risk of oral disease which decreased from a mean of 2.5 to 2.0 (sd=.70 for both, p=.04) self-management worries which decreased from a mean of 1.36 (sd=.66) to 0.57 (sd=.97); p=.002) and self-management fears which decreased from a mean of 2.2 (sd=.81) to 1.53 (sd=.97; p=.001). In contrast, non-AMI respondents showed mean increases (deterioration) from pre to post in all three domains.

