12 STATISTICAL CONSIDERATIONS

12.1 Study Hypotheses

- 1. The AMI-PM will produce better short term (T1) clinical outcomes than the Campaign (CA+PM) (AIM 1).
- 2. The CA+PM+AMI-PM will produce better mid-term (T2) and long-term (T3) clinical outcomes than the AMI-PM+CA+PM (AIM 2).
- 3. The AMI-PM will produce more change in mediating cognitive domains than the CA+PM.
- 4. Both AMI-PM+CA+PM and CA+PM+AMI-PM will result in no differences in change in mediating cognitive domains from T0 to T2.
- The greater the dosage (proportion of total talking points recorded for all domains in a tailored AMI; and exposure to campaign activities and messages), the better the outcomes.
- 6. We will investigate an exploratory hypothesis examining the effects of the intervention and sequence on oral health quality of life (a secondary outcome), as well as on clinical outcomes.

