12.4 Final Analysis Plan

The usual inspection for outliers and influential data points will be conducted along with summary statistics and evaluations of distributions of the data. We have experience with the clinical outcome measures, which have approximately normal distributions. In the case of non-normal data, we will use standard transformations (e.g., log) or explore alternatives (e.g., non-parametric approaches or other distributions such as Poisson).

Period 1: parallel arm phase: Standard approaches for a parallel 2-arm randomized study will be conducted for the first period of the sequence, across all buildings. This analysis allows direct comparison of the AMI vs. the Campaign approach for clinical outcomes (Study Hypothesis #1).

Periods 1 and 2: assessing sequence of interventions: Study Hypothesis #2, which sequence gives better clinical outcomes, will be addressed using repeated measures models. Depending on whether the outcome is continuous or dichotomous, we use general linear mixed models (GLMM) or general estimating equations (GEE), respectively, to fit a model with intervention and period effects using the MIXED procedure in SAS®. Each set of measures from the same person (e.g., gingival outcomes) are treated as a correlated cluster of data. An AR-1 correlation structure is

likely to be appropriate. Customized contrasts can be constructed to make comparisons

between time points. Time-varying covariates can be used in these models, and some missing data (under MAR or MCAR assumptions where applicable), is allowable.

Baseline & health status variables: As this study randomizes at the level of site and individuals are not randomized, we will likely stratify some results (or adjust in models) for demographics such as age, gender, marital status and individual characteristics such as health status, ADLs, depressive symptoms (CES-D) and oral health status (self-assessment). Any variable that shows potential for confounding or effect modification will be accounted for appropriately in all stages of the analysis.

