APPENDIX A: SCHEDULE OF EVENTS

Building A – Tailored intervention first followed by campaign

Visit	Activity	Timing	Compensation
1. – T0	Survey – 1 hour	Entry to study	\$15.00
2. – T0	Clinical assessment, skills assessment – 20 minutes	Entry to study	\$15.00
3.	Tailored educational session 45 min – 1 hour	Up to 45 days post T0	None
4. – T1	Survey – 1 hour	1-3 months after educational session	\$15.00
5. – T1	Clinical assessment, skills assessment – 20 minutes	1-3 months after educational session	\$15.00
	3 Campaign Events/Oral health fairs – 2-3 hours each	2-5 months after T1	None
6. – T2	Survey– 1 hour	1-3 months after campaigns	\$15.00
7. – T2	Clinical assessment, skills assessment – 20 minutes	1-3 months after campaigns	\$15.00
8. – T3	Clinical assessment, skills assessment, GOHAI – 20 minutes	6-7 months after T2	\$20.00

12/14/2010

Building B – Campaigns first followed by tailored intervention first

Visit	Activity	Timing	Compensation
1. – T0	Survey – 1 hour	Entry to study	\$15.00
2. – T0	Clinical assessment , skills assessment – 20 minutes	Entry to study	\$15.00
	3 Campaign Events/Oral health fairs – 2-3 hours total	3-6 months after study entry	None
3. – T1	Survey– 1 hour	1- 3 months after campaigns completed	\$15.00
4. – T1	Clinical assessment , skills assessment – 20 minutes	1- 3 months after campaigns completed	\$15.00
5.	Tailored educational session 45 min. to 1 hour	Up to 45 days after T1	None
6. – T2	Survey– 1 hour	1-3 months after educational session	\$15.00
7. – T2	Clinical assessment, skills assessment – 20 minutes	1-3 months after educational session	\$15.00
8. – T3	Clinical assessment, skills assessment, GOHAI – 20 minutes	6-7 months after T2	\$20.00

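### Section 12.4 names only AR-1 for the Hypothesis 2 model; fitted plainly with T0 as a response, it would make the plaque comparison at T2 or T3 too liberal (about 8-9% instead of 5%)

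*Combined protocol and SAP*

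**What the plan says.** Hypothesis 2 (Section 12.1) is "The CA+PM+AMI-PM will produce better mid-term (T2) and long-term (T3) clinical outcomes than the AMI-PM+CA+PM (AIM 2"). Section 12.4, under the heading on Periods 1 and 2, assigns it to repeated-measures models and proposes, for continuous outcomes, "to fit a model with intervention and period effects using the MIXED procedure in SAS". On correlation it says "Each set of measures from the same person (e.g., gingival outcomes) are treated as a correlated cluster of data". The covariance statement opens "An AR-1 correlation structure is" and, across a page break, continues "likely to be appropriate. Customized contrasts can be constructed to make comparisons" between time points.

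Nothing else is said about the covariance. There is no statement on equal or unequal variances, no alternative if AR-1 fits badly, and no mention of empirical (robust) standard errors for the mixed model. The role of T0 is not stated.

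Two other places bear on this. Section 2.1 reports the pilot plaque score (n=30) as moving from a mean at "baseline of 84% (sd=11.8%) to 58% (sd=31.2%) at follow-up"; the Gingival Index (GI) SD was 0.56 before and 0.47 after. Appendix A sets the visit timing, with T3 "6-7 months after T2" in both sequences and different gaps before that.

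**The concern.** The residual covariance sets the standard error of every sequence contrast in this model, and the model serves the second primary objective. In SAS MIXED, TYPE=AR(1) means one variance at all visits and a correlation that falls by a constant factor per visit step. An analyst who takes the text at face value would probably fit that.

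The plan's own pilot data do not look like that for plaque. Baseline scores were bunched near the top of the scale, and follow-up scores were widely spread. If the small T0 variance is pooled with larger follow-up variances, the fitted variance is too small for T2 and T3, and a comparison of sequences at those visits rejects too often. For a change from T0 the error goes the other way, because T0 is credited with more variance than it has. Appendix A adds unequal visit gaps that differ between sequences, which a decay by visit order does not describe.

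**Working it through.** **1. The plan's own figures.** No operating characteristic is stated for the Hypothesis 2 model. The nearest figure is the two-group t-test power in Section 12.2. Its lowest row reproduces: 0.20/0.47 = 0.426; 0.426 × √(123/2) = 3.337; Φ(3.337 − 1.96) = 0.916, against 91 stated. The other rows agree within two points. That calculation uses no repeated-measures covariance, so it does not bear on this point.

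**2. Are the pilot variances equal?** Paired-variance (Pitman-Morgan) test: t = (F − 1)√(n − 2) / (2√(F(1 − r²))), with n = 30. The correlation r is not given, so 0 to 0.5 is assumed.
- Plaque: F = 0.312²/0.118² = 0.097344/0.013924 = 6.99. At r = 0, t = 5.99 on 28 df; p < 0.00001 throughout.
- GI: F = 0.56²/0.47² = 1.42. t = 0.93 to 1.08; p = 0.36 to 0.29.

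A common variance is clearly contradicted for plaque, but not for GI.

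**3. Consequence under plain AR(1) with T0 as a response.** Let Σ be the true four-visit covariance, V the AR(1) matrix that the fit converges to, and c the contrast. Then ratio = √(c′Vc / c′Σc), and actual size = 2{1 − Φ(1.96 × ratio)}. Assumption: SD at T1, T2 and T3 equals the pilot follow-up SD.

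The zero-correlation case can be done by hand, because the fitted variance is then the mean of the four visit variances.
- Plaque: (0.013924 + 3 × 0.097344)/4 = 0.076489.
  - At T2 or T3: ratio = √(0.076489/0.097344) = 0.886; size = 8.2%.
  - Change T0 to T3: ratio = √(2 × 0.076489 / (0.013924 + 0.097344)) = 1.173; size = 2.2%.
- GI: (0.3136 + 3 × 0.2209)/4 = 0.244075.
  - At T2 or T3: ratio = √(0.244075/0.2209) = 1.051; size = 3.9%.

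Over the assumed correlations:

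| Contrast between sequences | Size at nominal 5% |
|---|---|
| Plaque at T2 or T3, AR-shaped correlation 0-0.7 | 8.2-9.2% |
| Plaque at T2 or T3, post-baseline correlation 0.3-0.7, baseline correlation −0.06 | 8.3-8.9% |
| Plaque change T0 to T3 | about 1-4% |
| GI at T2 or T3 | 3.6-3.9% |
| GI change from T0, AR-shaped correlation | 6.1-6.3% |
| GI change from T0, compound-symmetric correlation 0.2-0.7 | 0.6-4.1% |

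The −0.06 is (0.118² + 0.312² − 0.34²)/(2 × 0.118 × 0.312). It treats the planning SD of 0.34 as an SD of change, which Section 12.2 does not say. The low end for plaque change comes from equal correlation at all lags. At 0.3, for example, the fit is SD 0.2753 with ρ = 0.257. The fitted variance of change is 2 × 0.0758 × (1 − 0.257³) = 0.149, and the true one is 0.111268 − 2 × 0.3 × 0.118 × 0.312 = 0.089. The ratio is 1.29 and the size 1.1%.

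**4. Simulation check.** With 1,500 runs, 180 per arm and 25% dropout (Monte Carlo SE about 0.6 points), plain AR(1) gave plaque 8.5% at T2 and 9.5% at T3. Heterogeneous ARH(1) gave 5.9% and 4.7%. For GI, AR(1) gave 3.6% and 4.3%; ARH(1) gave 5.5% and 4.7%. In a separate simulation, an unstructured covariance gave 4.0-5.8% throughout.

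**5. Visit spacing.** Adding the Appendix A windows (45 days taken as 1.5 months):

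| Gap (months) | AMI-PM first | Campaign first |
|---|---|---|
| T0-T1 | 1-4.5 | 4-9 |
| T1-T2 | 3-8 | 1-4.5 |
| T2-T3 | 6-7 | 6-7 |

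With equal variances, complete data and an assumed decay of 0.80-0.95 per month, a sequence contrast at T2 or T3 alone stays at exactly 5.0%. The T2-to-T3 change is 7.0-8.0% at mid-range gaps and 11-13% at the shortest; the T0-to-T2 change is 3.9-4.7% and 1.9-3.4%.

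**6. T0 as a covariate.** The model then covers T1-T3 only. With equal SDs there, size at T2 or T3 is 5.0-5.8% for plaque and 5.0-6.3% for GI over the correlations tried.

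**The case against.** The best defence is that the plan commits to little. AR-1 is described as likely, not fixed. The text names a correlation structure and is silent on variances, and ARH(1), also available in SAS MIXED, has AR-1 correlation with unequal variances and brings the size close to nominal. Hypothesis 2 compares sequences at T2 and T3, and an analyst might well put T0 in as a covariate. The pilot had one follow-up, so the documents contain no SD for T2 or T3 in this design.

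All of that stands, and it rules out three stronger readings that a reader might infer:
- *That the plan prescribes a single-variance AR(1), so the Hypothesis 2 p-values are wrong.* The single variance is an inference from the plain software option, and the inflation also needs T0 as a response and model-based standard errors.
- *That both primary outcomes contradict AR-1.* The GI SDs are compatible with a common variance, and the direction of the error for GI change depends on a correlation the documents do not give.
- *That the visit schedule invalidates the T2 and T3 comparisons.* With complete data it affects change or averaged contrasts only. Section 5.3 also says that assessment timing is the same in both buildings, which conflicts with Appendix A; the two must be reconciled.

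The defence does not remove the gap. AR-1 is the only structure named, the plain option is the natural reading, and leaving the choice open means making it after the data are seen.

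**Conclusion.** The point holds as a conditional one and is worth correcting. If the Hypothesis 2 model is fitted as plain TYPE=AR(1) with T0 as a response and model-based standard errors, the pilot plaque SDs contradict its single variance. The plaque sequence contrast at T2 or T3 would then run at about 8-9% instead of 5%, and the plaque change from T0 to T3 at about 1-4%. For GI at a visit the effect is small (about 4%); for GI change the direction is unknown. These figures assume T1-T3 SDs equal to the pilot follow-up SD, the correlation ranges shown, and no building effect. They do not apply if T0 is only a covariate.

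This is not the largest threat to these p-values. Section 12.4 names only the person as the cluster. At the plan's ICC of 0.01-0.02 with 45 per building, the design effect is 1 + 44 × ICC = 1.44 to 1.88. Ignoring it gives size 2{1 − Φ(1.96/√1.44)} = 10% to 2{1 − Φ(1.96/√1.88)} = 15%. A better visit covariance does not cure that.

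**What to change.** Replace the AR-1 sentence in Section 12.4 with: *Residual covariance across visits is unstructured (TYPE=UN); if the model does not converge, a heterogeneous-variance structure (for example ARH(1) or CSH) is used.* Apply it to plaque and GI alike. Add a sentence saying whether T0 is a response or a covariate. Reconcile Section 5.3 with Appendix A on assessment timing. Make these changes in addition to accounting for building.

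Cost: two sentences and no change to data collection. With T0 as a response there are 4 × 5/2 = 10 covariance parameters; with T0 as a covariate, 3 × 4/2 = 6. The 270-360 participants support either. The unstructured form also needs no assumption about decay with visit order. The fallback structures do assume a correlation pattern, so they should remain fallbacks.

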Oral Health Self-Management Intentionality: Intention to perform the oral health self-management behaviors, a critical component of the IM model, will be assessed using the protocol described by Ajzen and Fishbein (1980) and Tedesco, et al. (1991) and adapted based on formative data. Participants will be asked to rate their intention to brush and floss daily using a five item four point Likert scale Alpha=.81.3.2.4 Intervention Variables

Exposure to norms based campaign: *Dosage* will be assessed by: (a) reported attendance at each campaign activity (three), and (b) number of activities respondent participated in at each event (passport).

Number of focal points addressed in intervention: This is a count based on respondents' score below the cutoff points for main cognitive and behavioral domains measured and addressed in the intervention.

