Intervention variables: As all subjects are exposed to the same interventions, it is of interest to unpack the intervention into 1) dosage (percent of talking points covered for all focal points (domains) addressed in the intervention, and 2) exposure to focal point messages during campaigns. Study Hypothesis #5, regarding dosage of interventions, will be assessed by creating an ordinal scale that measures an individual's exposure to talking points through participation in the AMI and exposure to messages via campaigns, thus creating a measure of dosage. We will then assess if dosage predicts better outcomes. This can be done directly (e.g., compare mean gingival scores across dosage levels with ANOVA) or dosage can be used as a predictor variable in the statistical models and causal pathway analyses. Oral health skills/Practice-to-Mastery (a 4 point Likert scale) and focal points (count variable) can be analyzed using similar techniques and approaches.

MFFD layout: N at the beginning of study			
	Sequence	N	
Building 1	A:B	60	
Building 2	B:A	60	
Building 3	A:B	60	
Building 4	B:A	60	
Building 5	A:B	60	
Building 6	B:A	60	

Secondary Outcome of General Oral Health Assessment Inventory (GOHAI): We will conduct a set of secondary analyses with GOHAI as a continuous outcome. It will also be incorporated into our statistical/mediator models as predictor to see if it acts as an effect modifier.

Cognitive Mediators: The following variables will be incorporated into the causal pathway analysis to address example hypotheses #3 and #4: knowledge, oral health beliefs/norms, social support, oral hygiene behaviors, fears/worries, practice to mastery, and behavioral intentions. We will use longitudinal mediation to compared the efficacy of AMI-PM+CA+PM to CA+PM+AMI-PM in terms of whether they differ significantly in the amount of change that they engender in the gingival index and plaque score, indirectly through the mediators measured in our model.

outcomes.

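### Hypothesis 5 is tested on one dose scale covering both components; applied at T1 without a condition term, it can present a condition difference as a dose-response, or hide or reverse one.

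*Combined protocol and SAP*

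**What the plan says.** Hypothesis 5 (section 12.1) is a single claim about two exposures: "proportion of total talking points recorded for all domains in a tailored AMI; and exposure to campaign activities and messages". No time point is attached to it.

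The Intervention variables paragraph of section 12.4 first separates these into percent of AMI talking points and exposure to campaign messages. It then brings them together for the test by "creating an ordinal scale that measures an individual's exposure to talking points through participation in the AMI and exposure to messages via campaigns". How the two are combined and where the levels are cut is not stated.

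The paragraph offers two analyses. One is to "compare mean gingival scores across dosage levels with ANOVA", given as an example and without a condition term. In the other, "dosage can be used as a predictor variable in the statistical models and causal pathway analyses". The repeated-measures model described earlier in section 12.4 is said "to fit a model with intervention and period effects using the MIXED procedure in SAS".

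The intervention-variables text in section 3.2 measures campaign dose by attendance at each of three activities and by "number of activities respondent participated in at each event (passport" record. AMI dose is a percentage from one tailored session.

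Section 4 and Appendix A fix the order. Condition 1 has the AMI session before T1 and the fairs after it. Condition 2 has the fairs before T1 and the AMI session after it.

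**The concern.** At T1 nobody has received both components. Any common scale then compares AMI scores in one condition with campaign scores in the other, so the level a person falls in may partly identify the condition. Hypothesis 1 predicts that the conditions differ in outcome at this same time point, and section 12.2 powers the trial on this period. An analysis of outcome by dose level that leaves out condition can pick up that difference.

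The direction depends on which component scores higher on the scale. If the better component scores higher, the result looks like support for Hypothesis 5. If it scores lower, a real dose effect is masked or reversed.

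This is distinct from self-selection into voluntary fairs. It arises even if dose within each component is unrelated to anything else.

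At T2 and T3 the issue is different. Both conditions have been offered both components, and one merged scale gives one answer that cannot be attributed to either. The first objective (section 3.1) asks for separate as well as combined effectiveness.

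**Working it through.** **Inputs from the documents.** Two-sided alpha 0.05. Retained N is 135 per condition. The conservative plaque row in section 12.2 has difference 0.20, SD 0.47 and N = 123 per group, with stated power 91%. Hypothesis 5 has no figure of its own, so this condition difference is borrowed for illustration.

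**Reproducing the plan's figure.** d = 0.20/0.47 = 0.426. Noncentrality = 0.426 × √(123/2) = 3.34. Power ≈ Φ(3.34 − 1.96) = 0.916, or 0.914 by the noncentral t. The stated 91% is reproduced.

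**Assumptions.** The documents give no dose distributions, so the means below are assumed. There is no dose effect within either component. Outcome is in SD units, scored so that higher is better, with the AMI-first condition better by d. Dose has four levels cut at pooled quartiles. There is no clustering. Each setting has 2,000 simulated trials.

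| T1 setting, d = 0.43 | Correlation of level with condition | ANOVA | Trend, no condition term | Trend with condition |
|---|---|---|---|---|
| Same distribution | 0.00 | 4.6% | 4.4% | 4.6% |
| Means 0.65 AMI, 0.55 campaign | 0.21 | 8.4% | 11.0% | 4.8% |
| Means 0.85 AMI, 0.50 campaign | 0.71 | 51.6% | 68.8% | 5.0% |
| Means 0.90 AMI, 0.50 campaign among attenders, 25% non-attenders | 0.80 | 67.4% | 79.0% | 5.2% |
| Means 0.50 AMI, 0.70 campaign | −0.41 | 19.6% | 30.3%, all in the wrong direction | 5.3% |

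**Closed-form check of the trend column.** With equal groups, a 0/1 condition indicator has SD 0.5. If r is the correlation of level with condition, the correlation of level with outcome is ρ = r × 0.5d / √(1 + d²/4), and the noncentrality is ρ√270 / √(1 − ρ²).

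- r = 0.71: ρ = 0.71 × 0.213/1.022 = 0.148; noncentrality 2.45; power ≈ Φ(0.49) = 69% (simulated 68.8%).
- r = 0.80: ρ = 0.166; noncentrality 2.77; power ≈ Φ(0.81) = 79% (simulated 79.0%).
- r = 0.21: ρ = 0.044; noncentrality 0.72; two-sided rejection ≈ 11% (simulated 11.0%).

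The false-positive rate thus depends on two quantities: the condition difference d, and the correlation r of the scale with condition. If either is zero, it is nominal.

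**Other settings.**
- Fixed cuts at 0.25, 0.5 and 0.75, truncated-normal doses (AMI mean 0.8 or 0.9, campaign mean 0.4 or 0.6), d = 0.42: about 32-75% for trend and 23-65% for ANOVA. With d = 0.2: 11-25% for trend and 9-16% for ANOVA.
- No condition difference, quartile cuts: 4.3-6.0% across all three tests.
- d = 0.74 (the pilot plaque row, 0.25/0.34), two clearly separated settings: 95-99.8% without a condition term.
- T2, both exposures summed, equal uptake in the two conditions: correlation with condition 0; rejection 4.4-5.4%.

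**The case against.** The strongest reply is that the plan is under-specified here rather than wrong.

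- **Time point.** Hypothesis 5 does not mention T1, and a scale spanning both components fits an analysis after T2 at least as well. This stands: at T2 with equal uptake the link with condition vanishes. But T1 is not excluded either.
- **Combination rule.** A reader might infer that the two exposures are added. The plan does not say so, and an ordinal scale over two exposures can be built in other ways.
- **Units.** Campaign messages derive from the same domain scripts as the AMI (section 6), so a shared unit of domain messages is conceivable. The plan does not define one.
- **Model.** The second option may keep an intervention effect, which would remove the T1 problem. It is only one of two permitted routes, and the ANOVA carries no such term.
- **General safeguard.** Section 12.4 also states: "Any variable that shows potential for confounding or effect modification will be accounted for appropriately in all stages of the analysis". That sentence sits under baseline and health-status variables and does not name condition for the dose analysis.
- **AMI variation.** A reader might infer that scripted delivery makes AMI dose nearly constant, so that after T2 the scale mostly ranks fair attendance. The documents do not support this. The AMI is tailored to domains below cut-off (section 6), and people who miss one intervention may be retained (section 5.3), so AMI dose could vary widely.
- **Magnitude.** The high rates reflect assumed separation between the dose distributions. This is correct, and the range has to start at 5%.

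**Conclusion.** The concern holds in a conditional form. One of the two permitted analyses, used at T1, lets a condition difference enter the Hypothesis 5 result if the two dose distributions differ on the scale. At a condition difference of about 0.42 SD the false-positive rate runs from about 5% (same distributions) through 8-11% (small shift) to roughly 25-80% (clear separation). With condition in the model it is about 5%. These figures rest on assumed doses and ignore clustering by building.

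It would go too far to say that the arm difference will appear as a dose-response. The plan does not commit to T1, to a sum, or to omitting condition, and the direction can go either way. It would also go too far to say that the component doses cannot be separated: sections 13 and 16.3 show that AMI and passport data are recorded separately. It is the merged scale that cannot separate them at T2 and T3.

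Hypotheses 1 and 2 are unaffected. This is a worthwhile, inexpensive correction to an analysis outside the primary comparison.

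**What to change.** In section 12.4, Intervention variables:

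1. Replace the single scale with two dose variables: AMI dose (percent of talking points) and campaign dose (fairs attended, and stations or messages from the passport). Define the scoring of each.
2. State the time points for Hypothesis 5.
3. At T1, test each dose only within the condition that received that component.
4. At T2 and T3, enter both doses together with condition and building in the model, and report two slopes in place of the unadjusted ANOVA. Buildings are nested within condition, so state how building is entered.

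The cost is plan wording only, since the data are already collected. The result is two estimates rather than one, each less precise at T1: with 135 rather than 270 people and similar dose spread, the standard error is about √(270/135) = 1.41 times as large. None of this removes self-selection in voluntary fair attendance, so the slopes remain observational.

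### The plan lets Hypothesis 5 (dosage) be tested by an ANOVA of gingival means with no stated adjustment, although dosage is not randomised

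*Combined protocol and SAP*

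**What the plan says.** Hypothesis 5 in section 12.1 is directional: the greater the share of AMI talking points covered and the greater the "exposure to campaign activities and messages), the better the outcomes".

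Section 12.4 (Intervention variables) builds the exposure measure by "creating an ordinal scale that measures an individual's exposure to talking points through participation in the AMI and exposure to messages via campaigns". It then allows two analyses. The direct one is, as an example, to "compare mean gingival scores across dosage levels with ANOVA". The other follows in the same sentence: "or dosage can be used as a predictor variable in the statistical models and causal pathway analyses". Neither is named as the analysis of record. For the ANOVA no baseline value, building term, covariate or time point is given.

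The preceding paragraph of 12.4 (Baseline & health status variables) deals with confounding in general. Because individuals are not randomised, "we will likely stratify some results (or adjust in models") for demographics, health status, ADLs, depressive symptoms and self-assessed oral health. It adds: "Any variable that shows potential for confounding or effect modification will be accounted for appropriately in all stages of the analysis".

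On where dosage comes from, section 5.4.1 randomises buildings only. Campaign exposure is attendance at the fairs and the number of activities joined (the Intervention Variables text at the end of 3.2.3), and any resident may come (section 6). AMI dosage is the percentage of talking points covered in a session that staff deliver and tailor to the participant (sections 6 and 12.4).

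**The concern.** Dosage arises after randomisation, and its campaign part is chosen by the participant. Residents who attend more fairs may already have healthier gums, or may be those most worried about their mouths. A comparison of follow-up means across dosage levels would carry that baseline difference into the result. In the first case it can produce the predicted gradient with no dose effect at all; in the second it can hide a real benefit.

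The variable that would carry most of this, the T0 Gingival Index, is measured on everyone but is absent from the covariates 12.4 names. So is building, although mean exposure may well differ between buildings because each runs its own fairs.

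At stake is the conclusion on a numbered study hypothesis. An analyst following the plan could take the unadjusted route, or choose after seeing both results.

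**Working it through.** The documents give no sample size, power or error rate for Hypothesis 5, so there is no figure to reproduce.

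**Inputs from the documents**
- Completers: 135 per sequence, 45 per building (section 12.2), so 2 × 135 = 270 in six buildings.
- Two-sided α of 0.05 (stated in 12.2 for the primary power table only).
- ICC 0.01 or 0.02 (12.2).

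**Assumptions not in the documents**
- Correlation r_d between dosage and T0 Gingival Index, 0 to 0.4 in size, with worse gums going with less exposure.
- Correlation r_b between T0 and follow-up Gingival Index, 0.3 to 0.7.
- Dosage cut into three equal levels (12.4 gives no number of levels).
- Equal variance at T0 and follow-up, and no true dose effect.

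**Mechanism.** With no dose effect, selection alone gives a dosage-to-follow-up correlation of size r_d × r_b. At r_b = 0.5 this is 0.1 × 0.5 = 0.05, 0.2 × 0.5 = 0.10 and 0.3 × 0.5 = 0.15.

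**Rejection rate of the unadjusted ANOVA** (4,000 simulated trials per cell, n = 270, no true effect):

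| r_d (size) | r_b = 0.3 | r_b = 0.5 | r_b = 0.7 |
|---|---|---|---|
| 0 | 4.6% | 4.3% | 4.8% |
| 0.1 | 6.6% | 8.3% | 13.3% |
| 0.2 | 11.1% | 23.5% | 43.4% |
| 0.3 | 20.0% | 47.9% | 79.5% |
| 0.4 | 33.7% | 75.7% | 97.0% |

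With the T0 score as a covariate, the rate is 4.3% to 5.7% in every cell.

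**Sensitivity to the number of levels.** A separate simulation with four levels (3,000 trials, r_b = 0.5) gave 21.5% at r_d = 0.2 and 46.5% at 0.3, against 5.8% and 5.0% after T0 adjustment. The result does not hinge on how the scale is cut.

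**Building.** With no individual selection, mean dosage varying between buildings and ICC 0.01 to 0.02, the unadjusted ANOVA rejects in 6.1% to 8.3% of trials. With T0 score and building in the model it rejects in 5.0% to 5.4%. This is a smaller effect, but T0 adjustment alone does not remove it (5.9% to 8.0%).

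**If change from T0 were compared instead.** The plan does not say whether level or change is meant. With equal variances, the induced correlation between dosage and change is r_d(1 − r_b)/√(2(1 − r_b)) in size. At r_b = 0.5 and r_d = 0.2 this is 0.2 × 0.5/1 = 0.10: the same size as for the level, with the opposite sign. Unadjusted change scores therefore do not solve the problem.

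**The case against.** The strongest reply is that the plan does not commit to this ANOVA. A reader might infer that Hypothesis 5 will be tested on raw means. The text does not support that: the ANOVA is introduced permissively, as an example, with the model route as the stated alternative. The plan also promises, in general terms, to account for confounders at every stage. Both points stand, so this is a permitted weak route rather than a planned error. But the promise is not tied to Hypothesis 5, gives no rule for identifying or handling a confounder, and its examples omit the T0 outcome scores and building. It does not close the route.

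A reader might also infer that participants with more deficits receive more dosage. The documents do not support this. The count of focal points, based on respondents' "score below the cutoff points for main cognitive and behavioral domains", is a separate variable. AMI dosage is a percentage whose denominator is the participant's own focal points, and coverage depends partly on the interventionist. Self-selection describes fair attendance, and AMI dosage only in part.

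It is also fair to say that the magnitudes rest on correlations found nowhere in the documents, and that T0 adjustment restores the nominal rate here because T0 is the only individual-level confounder simulated. Both limits are accepted.

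Finally, Hypothesis 5 carries no AIM label and dosage appears in none of the three objectives. That limits the weight of the point but does not remove it.

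**Conclusion.** The point holds in this form: section 12.4 permits an ANOVA with no stated adjustment for a non-randomised and partly self-selected exposure, and nothing in the plan commits to adjusting for the T0 outcome score or building in that test.

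If that route is used and attendance is related to baseline gingival status, the result can be false in either direction. The size is unknown. With 270 completers and an assumed T0-to-follow-up correlation of 0.5, the false-positive rate is about 5% with no selection, about 8% at a dosage-baseline correlation of 0.1, 21-24% at 0.2 and 46-48% at 0.3. Over all the assumed cases with some selection it runs from about 7% to 97%. No single one of these figures should be read as the trial's error rate.

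Nothing here touches the randomised comparisons under Hypotheses 1 and 2. The change is worth making because it costs almost nothing and the data it needs are already collected.

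**What to change.** In section 12.4, delete the ANOVA option and commit Hypothesis 5 to the model route that the same sentence already allows. Regress the follow-up score on dosage, adjusted for:
- the T0 value of the same outcome (Gingival Index or Plaque Score);
- building, which also accounts for condition because each building follows one sequence;
- the T0 covariates already listed in 12.4.

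State the dosage levels and the follow-up time point in advance. Report the result as an association, since T0 adjustment does not remove unmeasured motivation. Separate terms for AMI and campaign dosage are optional; they would help at T1, when each condition has received only one component (Appendix A).

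The cost is a few lines of wording and minor programming, with no new data. The small downside is a weaker claim for Hypothesis 5.
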